2.2.2 Secondary Efficacy Endpoints

2. Device success rate at 24 hours to 7 daysⁱ, defined according to the Valve Academic Research Consortium-2 (VARC-2) guidelines as:³²
 - Absence of procedural mortality, **AND**
 - Correct positioning of a single prosthetic heart valve into the proper anatomical location, **AND**
 - Intended performance of the prosthetic heart valve, defined as the absence of patient-prosthesis mismatch and mean gradient < 20 mmHg (or peak velocity < 3 m/sec), **AND** No moderate or severe prosthetic valve regurgitation.
3. Hemodynamic performance at 24 hours to 7 days (discharge) and 1 year post procedure, including the following hemodynamic metrics as measured by transthoracic echocardiography (TTE) and assessed by an independent core laboratory:
 - Mean prosthetic valve gradient
 - Effective orifice area
 - Degree of prosthetic valve regurgitation (transvalvular, paravalvular, and total)

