Prosthetic valve thrombosis	Any thrombus attached to or near an implanted valve that occludes part of the blood flow path, interferes with valve function, or is sufficiently large to warrant treatment. *Valve-associated thrombus identified at autopsy in a patient whose cause of death was not valve related should not be reported as valve thrombosis.
Valve migration	After initial correct positioning, any observed movement (upward or downward) of the Evolut R within the aortic annulus from its initial position, with or without consequences.
Valve embolization	The Evolut R moves during or after deployment such that it loses contact within the aortic annulus
Ectopic valve deployment	Permanent deployment of the Evolut R in a location other than the aortic root
TAV in TAV deployment	Additional valve prosthesis is implanted within a previously implanted Evolut R because of sub-optimal device position and/or function, during or after the index procedure.
Hemolysis	Red cell destruction as evidenced by plasma free hemoglobin >50 mg/dl Minor hemolysis: No intervention required Major hemolysis: Requires intervention (e.g. iron supplements, transfusion, invasive intervention).
Frame fracture	Visual evidence on radiography or at explant of loss of contact between elements (cells) of the stent. Minor frame fracture: Does not require intervention, or is not associated with prosthetic valve dysfunction. Major frame fracture: Intervention required (e.g. reoperation, catheter re-intervention) or is associated with prosthetic valve dysfunction

PROSTHETIC VALVE ENDOCARDITIS

Any of the following:

1) Fulfillment of the following Duke criteria⁴⁷ for definite endocarditis:

- Histologic and/or microbiologic evidence of infection at surgery or autopsy, or
- 2 major criteria, or
- 1 major criteria or 3 minor criteria, or
- 5 minor criteria

Major and minor criteria are as follows:

Major Criteria:

- Blood cultures positive for Infective Endocarditis (IE)
 - Typical microorganisms consistent with IE isolated from two separate blood cultures, as noted below
 - Viridans streptococci, *Streptococcus bovis*, *Staphylococcus aureus*, or HACEK group
 - Community-acquired enterococci in the presence of a primary focus
 - Microorganisms consistent with IE isolated from persistently positive blood cultures defined as:
 - At least two positive cultures or blood samples obtained >12 hours apart, or

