 - All of three, or a majority of four or more separate cultures of blood, the first and last sample obtained > one hour apart
 - Single blood culture positive for *Coxiella burnetii* or an antiphase I IG antibody titer >1:800
- **Evidence of endocardial involvement**
 - Positive results of echocardiography for IE defined as:
 - Oscillating intracardiac mass on a valve or supporting structures in the path of regurgitant jets or on implanted material in the absence of an anatomic explanation, or
 - Abscess, or
 - New partial dehiscence of a valvular prosthesis
 - New valvular regurgitation (worsening or changing or pre-existing murmur not sufficient)

Minor Criteria:

- **Predisposition:** predisposing heart condition or intravenous drug use
- **Fever:** temperature >38°C
- **Vascular phenomena:** major arterial emboli, septic pulmonary infarcts, mycotic aneurysm, intracranial hemorrhage, conjunctival hemorrhages, and Janeway's lesions
- **Immunological phenomena:** glomerulonephritis, Osler's nodes, Roth's spots, and rheumatoid factor
- **Microbiological evidence:** positive blood culture but does not meet a major criterion (as noted above) or serological evidence of active infection with organism consistent with infectious endocarditis.
- **Echocardiographic findings:** consistent with IE but do not meet a major criterion as noted above

If only 1 major and 1-2 minor criteria are fulfilled, or if only 3-4 minor criteria are fulfilled, the event will be coded as "possible endocarditis"

- 2) Evidence of abscess, paravalvular leak, pus, or vegetation confirmed as secondary to infection by histological or bacteriological studies during a re-operation
- 3) Findings of abscess, pus, or vegetation involving the Evolut R at autopsy

E.3 Efficacy Event Definitions³²

PROSTHETIC VALVE DYSFUNCTION	
Stenosis: mild	
For subjects with BSA $\geq 1.6 \text{ m}^2$: Mean aortic gradient ≥ 20 and ≤ 40 mmHg, EOA ≥ 0.8 and $\leq 1.1 \text{ cm}^2$ AND/OR DVI ≥ 0.25 and ≤ 0.35
 
For subjects with BSA $< 1.6 \text{ m}^2$: Mean aortic gradient ≥ 20 and ≤ 40 mmHg, EOA $\geq 0.6 \text{ cm}^2$ and $\leq 0.9 \text{ cm}^2$ AND/OR DVI ≥ 0.25 and ≤ 0.35

Stenosis: moderate/severe	
For subjects with BSA $\geq 1.6 \text{ m}^2$: Mean aortic gradient > 40 mmHg, EOA $< 0.8 \text{ cm}^2$ AND/OR DVI < 0.25
 
For subjects with BSA $< 1.6 \text{ m}^2$: Mean aortic gradient > 40 mmHg, EOA $< 0.6 \text{ cm}^2$ AND/OR DVI < 0.25

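### The endocarditis definition gives enterococcal bacteremia major credit on its typical-organism line only when a primary focus is present, and does not say which echo makes regurgitation new

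*Protocol*

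**What the plan says.** Protocol Appendix E says that sites and the Clinical Events Committee (CEC) code events from its definitions. In E.2, item 1 of the endocarditis definition is a count of criteria:

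- **Blood cultures (major).** Typical organisms in two separate cultures, including "Community-acquired enterococci in the presence of a primary focus". A separate route accepts any organism consistent with endocarditis if cultures are persistently positive.
- **Echo (major).** An oscillating mass (only if no anatomic explanation exists), an abscess, new partial dehiscence, or "New valvular regurgitation (worsening or changing or pre-existing murmur not sufficient".
- **Minor.** These include "predisposing heart condition or intravenous drug use", fever above 38°C, and a positive culture that falls short of a major criterion.
- **Definite.** Among other routes, "2 major criteria, or" and "1 major criteria or 3 minor criteria, or".
- **Possible.** The rule for this lesser category begins "If only 1 major and 1-2 minor criteria are fulfilled, or if only 3-4 minor criteria are fulfilled, the event will be coded as", and then names the category.

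Item 2, an alternative route, is "Evidence of abscess, paravalvular leak, pus, or vegetation confirmed as secondary to infection by histological or bacteriological studies during a re-operation".

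Appendix G gives codes 163 (definite) and 164 (possible), and separate codes 802 and 803 for sepsis. Table 7 in Section 5.7.2 makes prosthetic valve endocarditis reportable whether or not it is serious.

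**The concern.** The enterococcal line looks reversed. When a bloodstream infection already has a source, that is a reason to doubt that the valve is the source. Here the source is what earns the major criterion.

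The regurgitation line has a different fault: it leaves open what new is measured from. Section 5.3.6 and Appendix B.1 use baseline for the pre-implant echo, and against that exam a leak created by the implant is new. The protocol elsewhere treats such leak as part of prosthetic regurgitation (Section 2.2.2: "Degree of prosthetic valve regurgitation (transvalvular, paravalvular, and total").

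At stake is whether the endocarditis count reported for this device reflects infection of the valve. Section 5.7.7 guarantees CEC adjudication only for deaths and safety endpoint events. Endocarditis sits in E.2 among the other complications, so a literal coding by a site might never be reviewed.

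**Working it through.** There is no stated figure to reproduce. The check compares the criteria with each other and then counts cases.

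**1. What an alternative explanation does within the one definition**

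| Finding | Effect of an alternative explanation |
|---|---|
| Oscillating mass | Removes credit |
| Paravalvular leak under item 2 | Credit only if infection is confirmed |
| Community-acquired enterococci, two cultures | Required for credit on this line |
| New regurgitation | Not addressed |

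The enterococcal line is the only one that runs the opposite way.

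**2. Enterococcal bacteremia without a focus.** It fails the typical-organism line. It can still be major through persistently positive cultures: at least two more than 12 hours apart, or all of three, or a majority of four or more with first and last over an hour apart. Otherwise it is a minor criterion. So source-less cases lose credit on one line, not on every route.

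**3. Scenarios.** *Literal* takes the mixed route as printed (1 major or 3 minor). *And* reads it as 1 major and 3 minor, the reading that removes the overlap with possible. Cases b, c and e assume fever and count the predisposing heart condition; cases c and e assume the cultures are not persistently positive.

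| Case | Major, minor | Literal | And |
|---|---|---|---|
| a. Enterococci with focus + leak accepted as new | 2, 0 | Definite | Definite |
| b. Enterococci with focus + fever + predisposition, leak not counted | 1, 2 | Definite and possible | Possible |
| c. Culture as minor + fever + predisposition, leak not counted | 0, 3 | Definite and possible | Possible |
| d. Leak accepted as new, nothing else | 1, 0 | Definite | Neither |
| e. Leak accepted as new + culture as minor + fever + predisposition | 1, 3 | Definite | Definite |

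Case a is definite whichever way the mixed route is read, so repairing that route alone does not cure it. Case e shows that repairing the enterococcal line alone is also not enough if leak is accepted. Case c is coded definite by the literal text with neither criterion in play.

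**4. The counting rule.** Take 0 to 2 major and 0 to 6 minor criteria: 3 × 7 = 21 combinations.

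- Literal: any major (14) + no major with 3 or more minor (4) = 18 definite.
- And: 2 major (7) + 1 major with 3 or more minor (4) + no major with 5 or more minor (2) = 13 definite.
- Possible: 4 combinations, (1,1), (1,2), (0,3) and (0,4). All 4 are also definite under the literal text; none is under the and-reading.

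Changing only the enterococcal and regurgitation lines leaves those 4 conflicts in place.

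**5. Reach.** Endocarditis is not in the primary endpoint (Protocol 2.2.1), the Early Safety composite (Protocol 2.2.3; SAP 3.7.3) or any other SAP analysis (3.6 to 3.7.4).

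**The case against.** The strongest objection concerns the leak. A reader might infer that the definition accepts the implant's own paravalvular leak as evidence of infection. The documents do not say so. The line stands in a list of echo findings for endocarditis and requires that the regurgitation be new. Item 2, the one place where the definition names paravalvular leak, demands confirmation of infection. Moderate and severe leak has its own codes (192 to 195), and Appendix E.3 note 4 keeps valve dysfunction without clinical sequelae out of adverse event reporting. All of that stands as evidence of intent. It does not settle the matter, because item 2 is an alternative route that does not limit item 1, and no reference exam is given. The supportable statement is that the text is ambiguous.

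A reader might also infer that ordinary sepsis is coded definite by these two criteria. That is too broad. Case a needs a community-acquired enterococcus, two separate positive cultures, an identified focus and a leak accepted as new. The wider over-coding in case c comes from the counting rule.

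Finally, it can be said that source-less enterococcal cases are not lost, since persistent cultures can rescue them. This is correct and limits the harm in that direction. It does not explain why a focus should earn credit.

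**Conclusion.** The enterococcal wording is a stated rule that contradicts the logic of its own definition. This takes the primary focus to mean a source other than the valve, which is the natural reading, though the term is not defined. The regurgitation line is an ambiguity: miscoding through it depends on a site accepting procedural leak as new.

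The consequence is limited to how events divide between codes 163/164 and 802/803. No hypothesis test or SAP estimate changes.

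No reliable size can be given. A reader might multiply assumed rates: 2–5% bacteremia and 30–60% leak in 1000 subjects gives 1000 × 0.02 × 0.30 = 6 to 1000 × 0.05 × 0.60 = 30 subjects. Against an assumed 10 to 30 true cases, the coded count would be 36/30 = 1.2 to 40/10 = 4 times the true one. None of these rates is in the documents. The product assumes independence and that every leak counts as new, and it ignores the enterococcal share; an assumed 10–30% share reduces it to 0.6 to 9 subjects. If procedural leak is not counted, it is zero. These figures should not be used.

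**What to change.** Make three edits to Appendix E.2 together:

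1. **Enterococci.** Reword the line so that an identified other focus is not what earns major credit, and check the wording against the criteria that the protocol cites (reference 47), which were not available for this review.
2. **Regurgitation.** State that new is judged against the post-implant TTE at 24 hours to 7 days, so that leak present on that exam does not count. Do not add an ungraded clause for worsening: with no severity threshold, it would widen the criterion. Name a fallback for a missing or unreadable exam, for example the earliest readable post-implant echo before the episode and, failing that, criterion not assessable.
3. **Counting rule.** Reconcile the mixed route to definite with the possible rule so that no combination falls under both.

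After all three edits, and with the mixed route read as and, focus-explained enterococcal bacteremia with fever and a predisposing condition would be possible rather than definite (case c). If its cultures were persistently positive it would have 1 major and 2 minor criteria, which is also possible.

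The cost is a few lines of text and a notice to sites. The reference echo is already collected and read by the core laboratory. The drawback is that its window is only recommended (Table 3, note 3), so some subjects will lack a usable exam and will depend on the fallback.

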An integrated exam approach using color flow, pulsed-wave (PW), and continuous-wave (CW) Doppler is used to assess the severity of transvalvular and paravalvular aortic regurgitation (AR). Color flow Doppler imaging should be performed from the parasternal long and short-axis views, and the apical long-axis and/or 5-chamber views. In the short axis view, color imaging should be performed just below the skirt and frame to assess paravalvular regurgitation, and at the coaptation point of the leaflets for transvalvular (central) regurgitation.⁴²

If AR is seen by color Doppler, a CW Doppler recording of the regurgitant signal should be obtained for measurement of pressure half-time and assessment of jet density. If the degree of AR by color Doppler appears more than mild by visual estimate, the velocity in the proximal descending aorta should be recorded with PW Doppler. In addition, the right ventricular outflow tract diameter (RVOT) and RVOT velocity time integral (VTI) should be measured to allow derivation of regurgitant volume and fraction.

The degree of transvalvular, paravalvular, and total (transvalvular plus paravalvular) AR will be graded as none, trace, mild, moderate, and severe based on the synthesis of the Doppler parameters shown in Table 14.^{36,37} The category of “trace” should be used in cases where regurgitation is barely detectable by color Doppler.³⁶ Regurgitant signals observed to originate within the stent will be considered transvalvular, and regurgitant signals observed to originate outside the stent will be considered paravalvular.

Table 14. Parameters for evaluation of the severity of aortic regurgitation

Parameter	Mild	Moderate	Severe
Jet width in central jets (% LVOT diameter): color ¹	Narrow ($\leq 25\%$)	Intermediate (26% - 64%)	Large ($\geq 65\%$)
Jet density: CW Doppler	Incomplete or faint	Dense	Dense
Jet deceleration rate (PHT, ms): CW Doppler ²	Slow (>500)	Variable (200 – 500)	Steep (<200)
LVOT flow vs pulmonary flow: PW Doppler	Slightly increased	Intermediate	Greatly increased
Diastolic flow reversal in descending aorta: PW	Absent or brief early diastolic	Intermediate	Prominent, holodiastolic
Circumferential extent of prosthetic paravalvular regurgitation (%)	<10	10 – 19	≥ 20
Quantitative Parameters			
Regurgitant volume (ml/beat)	<30	30 – 59	≥ 60
Regurgitant fraction (%)	<30	30 – 49	≥ 50

PHT = pressure half-time

B.4.5 Assessment of Mitral Regurgitation

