APPENDIX E. DEFINITIONS: SAFETY ENDPOINTS AND EFFICACY EVENTS

Definitions of adverse events to be evaluated as clinical safety endpoints, other TAVI-related complications, and efficacy events are provided in Sections E.1, E.2, and E.3, respectively. Site investigators and the CEC will code events according to these definitions, using the associated code list provided in appendix G, Event Code List.

E.1 Safety Endpoint Definitions³²

Mortality	
Cardiovascular mortality	
Any of the following criteria:
 
 1) Death due to proximate cardiac cause (eg, myocardial infarction, cardiac tamponade, worsening heart failure) 2) Death caused by non-coronary vascular conditions such as neurological events, pulmonary embolism, ruptured aortic aneurysm, dissecting aneurysm, or other vascular disease 3) All procedure-related deaths, including those related to a complication of the procedure or treatment for a complication of the procedure 4) All valve-related deaths including structural or nonstructural valve dysfunction or other valve-related adverse events 5) Sudden or unwitnessed death 6) Death of unknown cause
Non-cardiovascular mortality	Any death in which the primary cause of death is clearly related to another condition (eg, trauma, cancer, suicide).

Myocardial Infarction	
Periprocedural MI (≤72 h after the index procedure)	
New ischemic symptoms (e.g, chest pain or shortness of breath), or new ischemic signs (e.g, ventricular arrhythmias, new or worsening heart failure, new ST-segment changes, hemodynamic instability, new pathological Q-waves in at least 2 contiguous leads, imaging evidence of new loss of viable myocardium or new wall motion abnormality) AND
 
Elevated cardiac biomarkers (preferable CK-MB) within 72 h after the index procedure, consisting of at least 1 sample post procedure with a peak value exceeding 15x as the upper reference limit for troponin or 5x for CK-MB. If cardiac biomarkers are increased at baseline (>99th percentile), a further increase in at least 50% post procedure is required AND the peak value must exceed the previously stated limit.

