Paravalvular regurgitation: moderate	Moderate paravalvular regurgitation (per echo criteria in CIP)
Paravalvular regurgitation: severe	Severe paravalvular regurgitation (per echo criteria in CIP)
Transvalvular regurgitation: moderate	Moderate paravalvular regurgitation (per echo criteria in CIP)
Transvalvular regurgitation: severe	Moderate or severe transvalvular regurgitation (per echo criteria in CIP)

Notes:

1. DVI = Doppler Velocity Index (LVOT VTI/valve VTI)
2. For subjects LVOT diameter > 2.5 cm, the DVI criteria for significant (moderate or severe) stenosis is 0.2
3. Reporting of prosthetic valve dysfunction will be based on core lab values (if available).
4. Prosthetic valve dysfunction events are not reported as adverse events, unless the dysfunction is accompanied with clinical sequelae at the time of event detection, and the clinical sequelae are chronologically and physiologically associated with the dysfunction. However, prosthetic dysfunctions that are associated with adverse events, and that meet the definition of a serious adverse event, should be reported as such.

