- 172 Atria-ventricular block, 3°

- 173 LBBB
- 174 RBBB
- 175 Left anterior fascicular block
- 176 Left posterior fascicular block
- 180 Atrial fibrillation
- 181 Atrial flutter
- 182 Junctional rhythm (<100 bpm)
- 183 Junctional rhythm (≥100 bpm)
- 184 Sinus bradycardia (<50 bpm)
- 185 Supraventricular tachycardia
- 186 Ventricular fibrillation
- 187 Ventricular premature beats
- 188 Ventricular tachycardia
- 189 Other arrhythmia

Prosthetic Valve Dysfunction

- 190 Mild stenosis
- 191 Moderate/severe stenosis
- 192 Moderate paravalvular regurgitation
- 193 Severe paravalvular regurgitation
- 194 Moderate transvalvular regurgitation
- 195 Severe transvalvular regurgitation

Other Implantation/Catheterization Procedure-Related Adverse Events

- 200 Brachial plexus injury
- 201 Hypovolemia
- 202 Hypotension requiring intervention
- 203 Air embolism
- 204 Venous thrombosis, definite
- 205 Venous thrombosis, suspected
- 206 Metabolic acidosis
- 207 Catheter induced arrhythmia
- 208 Hemothorax
- 209 Radiation-induced erythema
- 210 Other implantation/catheterization

Other Cardiac Adverse Events

- 300 Cardiac arrest
- 301 Congestive heart failure
- 302 Cardiogenic shock
- 303 Valvular regurgitation, mitral
- 304 Valvular regurgitation, tricuspid
- 307 Syncope
- 308 Palpitations
- 309 Cyanosis
- 310 Chest pain
- 311 Pericardial effusion, hemorrhagic
- 312 Pericardial effusion, non-hemorrhagic
- 313 Intracardiac mass
- 399 Other cardiac event

Respiratory/Pulmonary Adverse Events

- 400 Respiratory arrest
- 401 Pneumothorax
- 402 Chronic pulmonary disease
- 403 Bronchospasm/asthma
- 404 Pleural effusion
- 405 Hemoptysis
- 406 Respiratory failure
- 407 Atelectasis
- 408 Hemothorax
- 409 Respiratory insufficiency
- 410 Apnea/hypoventilation
- 499 Other respiratory/pulmonary

Other Neurologic Adverse Events

- 500 Seizure(s)
- 502 Meningitis, infectious
- 504 Headaches
- 505 Dizziness
- 599 Other central nervous system

Gastrointestinal Adverse Events

600 Vomiting
601 Diarrhea
602 Protein losing enteropathy
603 Liver disease
604 Liver failure
699 Other gastrointestinal

1002 Rash
1003 Contrast reaction/allergy
1004 Medication reaction/allergy
1099 Other allergic reaction

Other

1200 Multi organ failure
1299 Other

Hematologic/Oncologic Adverse Events

700 Cancer/malignancy
701 Coagulopathy
702 Anemia (Hgb <10g or Hct <30%)
703 Thrombocytopenia
704 Transfusion reaction
799 Other hematologic/oncologic

Infection Adverse Events

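### Protocol Appendix E.3: the two transvalvular regurgitation definitions do not match their labels, so codes 194 and 195 can be misassigned when the text is applied literally

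*Protocol*

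**What the plan says.** Appendix E opens by making its definitions operative: "Site investigators and the CEC will code events according to these definitions", with the codes taken from Appendix G. The prosthetic valve dysfunction table in E.3 has four regurgitation rows.

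- The moderate paravalvular row is defined as "Moderate paravalvular regurgitation (per echo criteria in CIP", and the severe paravalvular row as "Severe paravalvular regurgitation (per echo criteria in CIP". Both agree with their labels.
- The row labelled "Transvalvular regurgitation: moderate" carries the same text as the moderate paravalvular row.
- The row for severe transvalvular regurgitation reads "Moderate or severe transvalvular regurgitation (per echo criteria in CIP".

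The echo criteria to which these rows point are in Appendix B.4.4. That section separates location by jet origin: "Regurgitant signals observed to originate within the stent will be considered transvalvular", and signals from outside the stent count as paravalvular. It also keeps the grades apart: regurgitation "will be graded as none, trace, mild, moderate, and severe based on the synthesis of the Doppler parameters". Appendix G gives code 194 the label "Moderate transvalvular regurgitation" and reserves code 195 for severe transvalvular regurgitation.

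Two notes under the E.3 table limit its reach. Note 3 bases dysfunction reporting on core-lab values where these exist. Note 4 keeps dysfunction out of adverse event reporting unless it has associated clinical sequelae, or is associated with adverse events and meets the serious-event definition.

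**The concern.** Leak through the prosthesis and leak around it are different device findings, and the protocol keeps them apart in its hemodynamic endpoint (Protocol 2.2.2) and in B.4.4. In E.3 one definition names the wrong location and the other joins two grades. A coder who follows the definition text would record a leak around the valve as a leak through it, and would record a moderate transvalvular leak as severe. The study's objective is to document device performance, so a listing of coded valve-dysfunction events should be right on both location and grade. Protocol 5.7.2 requires a code number for every reportable adverse event, so the wording could enter the database for events that are clinically important enough to be reported.

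**Working it through.** The plan states no figure on this point, so there is nothing to reproduce. The check is a comparison of texts followed by a count.

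**Step 1. Definitions against labels.** Inputs: the E.3 rows and the Appendix G codes.

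| Code | Label in Appendix G | Condition in E.3, read literally | Agreement |
|---|---|---|---|
| 192 | Paravalvular, moderate | Paravalvular, moderate | Yes |
| 193 | Paravalvular, severe | Paravalvular, severe | Yes |
| 194 | Transvalvular, moderate | Paravalvular, moderate | Wrong location |
| 195 | Transvalvular, severe | Transvalvular, moderate or severe | Two grades merged |

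**Step 2. Extent over all grade pairs.** B.4.4 has five grades for each location, so there are 5 × 5 = 25 pairs of paravalvular grade (P) and transvalvular grade (T).

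- Code 194, literal rule: P = moderate, 5 pairs, the same pairs as code 192. Intended rule: T = moderate, 5 pairs. The two overlap in 1 pair (both moderate). So 5 − 1 = 4 pairs are falsely coded 194 and 5 − 1 = 4 true ones are missed.
- Code 195, literal rule: T = moderate or severe, 5 + 5 = 10 pairs. Intended rule: T = severe, 5 pairs. So 10 − 5 = 5 pairs are overstated as severe.
- Pairs with at least one wrong code: the 4 with P moderate and T not moderate, plus all 5 with T moderate, which gives 4 + 5 = 9 of 25.
- With each definition matched to its label: 0 of 25.

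These are counts of grade pairs. They say nothing about how many patients fall in each.

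**Step 3. Where the codes go.**

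- Primary endpoint (SAP 3.6.5): deaths from the adjudication form.
- Device success (SAP 3.7.1.4): total regurgitation from the core-lab form.
- Hemodynamic performance (SAP 3.7.2.4): core-lab data.
- 30-day safety composite (SAP 3.7.3.4): codes 102 to 107, 110, 114 to 115, 120 to 127 and 152, the death form, and catheter or surgical interventions on the valve.

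None of these uses codes 190 to 195, and the SAP specifies no table of them.

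**Step 4. Does Note 3 settle it?** Only in part. It says which echo reading to use, not which code that reading receives: a core-lab grade of moderate paravalvular still satisfies the text of the moderate transvalvular row. In addition, echocardiograms for the core lab are scheduled after implant only at 24 hours to 7 days and at 1 year (Protocol 5.3.6), so dysfunction found at another time may have no core-lab value.

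**The case against.** The strongest reply is that little can go wrong in practice. The row labels in E.3 and the code labels in Appendix G are correct, and both faulty cells refer the reader to echo criteria that separate location and grade properly. A coder would have to set all three aside to give a paravalvular jet code 194. Few events would be exposed: Note 4 restricts adverse event reporting, and Table 7 in Protocol 5.7.2, which lists the events reportable whatever their seriousness, does not include valve regurgitation. The events committee must adjudicate only deaths and safety endpoint events (Protocol 5.7.7), so its coding of 194 and 195 is optional. Where the core lab has read the echo, it reports transvalvular, paravalvular and total grades as separate variables (Appendix B.5).

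All of this stands as a limit on the consequences. It does not remove the error: the definition text is what coders are told to apply, and nothing in the Protocol or SAP corrects it.

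Two stronger readings are tempting. A reader might infer that every moderate leak seen on echo would be miscoded. The documents do not support that, because most echo findings never become coded events and a coder may follow the label. A reader might also infer that the study would publish two conflicting regurgitation results. No planned analysis would produce the second one.

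**Conclusion.** The point holds as an internal inconsistency of low severity, a drafting slip rather than a choice of design. Two of the four regurgitation definitions in E.3 contradict their own labels, B.4.4 and Appendix G. Under literal use, code 194 duplicates code 192, and every reportable moderate transvalvular leak also meets code 195; 9 of 25 grade pairs are affected. This assumes that coders apply the definition text rather than the label. The documents give no rate of reportable regurgitation events, so the effect cannot be stated as a percentage of subjects. It reaches only the coding and any tabulation of valve-dysfunction events. No endpoint, specified SAP analysis, sample size, power or alpha changes.

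**What to change.** Reconcile the two E.3 rows with B.4.4 and Appendix G: define moderate transvalvular as moderate transvalvular regurgitation and severe transvalvular as severe transvalvular regurgitation, each by the protocol's echo criteria and with core-lab values where available. Then review any events already coded 194 or 195 against the echo reading and recode where needed. The cost is a two-cell protocol correction and a check of what should be few records. The SAP needs no change.
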